7.5.3 Abnormal laboratory values

Any grade 3/4 laboratory abnormalities or any clinically significant grade 1/2 hematology or biochemistry laboratory value(s) should be recorded as an AE. Isolated laboratory abnormality without clinical significance should not be captured as AE if confirmed by the investigator. If an abnormal laboratory value or vital sign is associated with clinical signs and/or symptoms, the sign or symptom should be reported as an AE, and the associated laboratory value or vital sign should be considered additional information that must be collected on the relevant CRF. If the laboratory abnormality is a sign of a disease or syndrome, only the diagnosis needs to be recorded on the SAE Report Form or AE CRF.

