In RP6530-1401 study, a total of 58 patients were treated at Tenalisib 200 mg BID, 400 mg BID, 800 mg BID (Fasting) and 800 mg BID (Fed) in both dose escalation and expansion cohorts. Tenalisib demonstrated acceptable safety and tolerability profile up to 800 mg BID (Fasting). Reported DLTs included Grade 3 transaminitis, and Grade 3 skin rash. Tenalisib 800 mg BID (Fasting) was considered as maximum tolerated dose (MTD). Treatment related SAE were few and included pyrexia, raised international normalized ratio (INR), sepsis, skin infection, hypersensitivity, and diplopia secondary to neuropathy. Overall, Tenalisib has acceptable safety and tolerability profile up to 800 mg BID (Fasting).

• Pharmacokinetics (PK):

In RP6530-1301 study, maximum systemic exposures of Tenalisib were assessed on Cycle 1 Day 1 at doses 25 mg to 1200 mg BID; 600 and 800 mg TID. Based on C_{max} and AUC, dose proportionality was observed up to 400 mg dose. Dose related exposures were observed beyond 400 mg. There was no change in t_{max} on increasing doses however there was change in $t_{1/2}$. Steady state PK parameters of Tenalisib as determined on Cycle 2 Day 1 revealed no accumulation of Tenalisib. Similar PK profile was seen in RP6530-1401 study.

• Efficacy:

In RP6530-1301 study, Tenalisib demonstrated an ORR \approx 20% (CR: 7% and PR: 13%) in heavily pre-treated R/R patients with hematological malignancies. In RP6530-1401 study, response assessments of the thirty-five evaluable patients receiving at least two cycles of Tenalisib showed an ORR of 46% (CR: 9% and PR: 37%). Indication specific analysis showed an ORR of 47% (CR: 20%, PR: 27%) in PTCL and 45% (PR: 45%) in CTCL.

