3 TRIAL DESIGN

3.1 Trial End Points

Efficacy:

- Overall response rate (ORR): ORR is defined as sum of CR and PR rates as defined by iwCLL guideline for CLL (Hallek *et al.* 2018).
- Duration of response (DOR): DOR is defined as the interval from the first documentation of CR/PR to first documentation of definitive disease progression or death from any cause.
- Progression-free survival (PFS): PFS is defined as the interval from first dose to first documentation of definitive disease progression or death from any cause.

Safety:

• Adverse Event (AE), Grade 3/4 AEs, Serious Adverse Event (SAE)

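### Protocol 7.5.3 makes every Grade 3/4 laboratory abnormality an AE, then adds two rules without a grade limit that can keep such a value out of the Grade 3/4 AE count

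*Protocol*

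**What the plan says.** Protocol 7.5.3 has four sentences, in this order:

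1. "Any grade 3/4 laboratory abnormalities or any clinically significant grade 1/2 hematology or biochemistry laboratory value(s) should be recorded as an AE". Clinical significance is a condition for Grade 1/2 only.
2. "Isolated laboratory abnormality without clinical significance should not be captured as AE if confirmed by the investigator". No grade is mentioned.
3. Where symptoms accompany the value: "the sign or symptom should be reported as an AE, and the associated laboratory value or vital sign should be considered additional information". No grade is mentioned, and nothing says which grade the AE then carries.
4. Where the value belongs to a disease or syndrome, recording the diagnosis alone is enough.

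Protocol 3.1 and SAP 4.2 name Grade 3/4 AEs as a safety endpoint. Protocol 9.4.2 reports the incidence of Grade 3 and Grade 4 AEs. It also lists laboratory values separately and plans per-patient worst-grade tables for selected AEs and laboratory measurements.

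SAP 10.6.2 counts AE records by preferred term and maximum grade, with the safety set as denominator. SAP 10.6.3 plans descriptive statistics of absolute laboratory values, a listing, and a second listing of patients with abnormal values. It has no table by grade.

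SAP 5.1 and 6 state that 21 patients were enrolled in Stage 1, that the study has been closed, and that Stage 2 will not be performed.

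**The concern.** A site with an isolated Grade 3 value that its investigator considers unimportant is told by sentence 1 to record an AE and, read literally, by sentence 2 not to. A site with a Grade 3 value and a mild symptom can satisfy sentence 3 with an AE at the symptom's grade. Two sites could enter the same laboratory result differently, and neither would be breaching the protocol as written.

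Compared with sentence 1, the later sentences can only remove or lower a Grade 3/4 record and cannot create one. The Grade 3/4 AE incidence is built from those records, so any effect makes the drug look safer. Characterising safety is a secondary objective, and the cohort is small enough for a few records to matter.

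**Working it through.** **Step 1: the sentences side by side.**

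| Laboratory finding | Sentence 1 | Sentences 2 and 3, read literally | Possible AE record |
|---|---|---|---|
| Isolated Grade 3/4, investigator confirms no clinical significance | AE | Sentence 2: not an AE | Grade 3/4 AE, or none |
| Grade 3/4 with a Grade 1 symptom | AE | Sentence 3: the symptom is the AE | Grade 3/4 AE, or a Grade 1 AE |
| Grade 1/2, no clinical significance | Not required | Sentence 2: not an AE | None; no conflict |

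Only the last row is consistent. If sentence 2 is confined to Grade 1/2, the first row is resolved. The second row stays open, because sentence 3 is a separate rule.

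**Step 2: where the later rules would realistically be used.** Sentence 2 needs a judgement that the value has no clinical significance.

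- *Grade 3 ALT/AST.* Section 3.5.5 and Table 5 call for interrupting or withholding the drug, and Table 5 adds closer monitoring. Such a value is unlikely to be judged insignificant.
- *Grade 3 neutropenia.* Table 4 keeps the dose unchanged with at least weekly counts, so the judgement is plausible. Section 3.5.5, however, asks for interruption at Grade 3 or higher and names neutropenia. Those two passages need to be reconciled; this point takes no view on which should stand. The neutropenia example rests on Table 4.
- *Grade 3 thrombocytopenia with Grade 1 bleeding.* This is a row of Table 4, again with the dose unchanged. The protocol itself thus foresees a severe laboratory grade alongside a milder sign. Under sentence 3 the AE is the bleeding.

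**Step 3: is there a graded backstop?** Protocol 9.4.2 plans one, the worst grade per patient for selected laboratory measurements. SAP 10.6.3 does not carry it over. A Grade 3 value absent from the AE data would appear in the listings but in no graded table that the SAP specifies.

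**Step 4: size.** The documents give no Grade 3/4 laboratory rate and no omission rate, so only the scale can be shown.

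- One patient: 1/21 = 4.8 percentage points if all 21 enrolled received a dose; 1/20 = 5.0 if one did not. SAP 10.6.2 divides by the safety set, whose size is not given.
- This step applies to the rate for one preferred term, or to the any-Grade-3/4 rate when the patient has no other Grade 3/4 AE.
- Illustration with assumed values: let p be the true proportion with a Grade 3/4 laboratory event and f the fraction omitted or downgraded. Expected patients recorded = 21 × p × (1 − f), and the chance that none is recorded = (1 − p(1 − f))^21.

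| p | f | Expected recorded | Chance none recorded |
|---|---|---|---|
| 20% | 0 | 4.2 | 0.9% |
| 20% | 25% | 3.15 | 3.3% |
| 20% | 50% | 2.1 | 10.9% |
| 20% | 75% | 1.05 | 34.1% |

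At f = 50%, p = 10% gives 2.1 falling to 1.05, and p = 30% gives 6.3 falling to 3.15. None of these p or f values is an estimate for this trial.

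**The case against.** The strongest reply is that sentence 2 is simply the complement of the Grade 1/2 test in sentence 1, and that the specific rule for Grade 3/4 governs. That reading is natural and may be what was meant. But the text does not say so, and on that reading sentence 2 adds little, since sentence 1 already leaves out Grade 1/2 values that are not clinically significant.

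Sentence 3 can also be defended. It does not expressly cancel sentence 1, and a careful site could record both symptom and value. That is fair: the loss of grade is a permitted outcome, not a required one. Sentence 4 can preserve severity where the diagnosis is graded at least as high as the value, but 7.5.3 does not ask for that.

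A reader might infer that serious liver toxicity would drop out of the safety results, since the earlier T-cell lymphoma trial states: "Reported DLTs included Grade 3 transaminitis, and Grade 3 skin rash". The documents do not support this. Grade 3 ALT/AST leads to withholding and would hardly be confirmed as insignificant.

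A reader might also infer that toxicity data are lost. They are not: sentence 3 keeps the value on a case report form, and SAP 10.6.3 lists all laboratory data.

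Finally, safety is descriptive and the response endpoint is untouched. Rewording 7.5.3 cannot change records already made. Both points stand, and they shape the fix.

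**Conclusion.** Section 7.5.3 is internally inconsistent for Grade 3/4 laboratory values, and the inconsistency reaches a stated safety endpoint. Its effect can only be to lower the reported Grade 3/4 AE incidence relative to sentence 1. The realistic exposure is confined mainly to haematological values at which dosing continues.

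The size of any under-count cannot be derived. The 4.8-point step assumes that all 21 enrolled patients were dosed, and no particular shortfall should be read into it. The problem concerns the AE tables, not the survival of the data, and it is recoverable because the laboratory values are held. It should be put right before the safety tables are produced, since the SAP as written has no graded laboratory table that would reveal it.

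**What to change.** **Reconcile the text.** State in 7.5.3 that the exemption for isolated abnormalities covers Grade 1/2 only, and that a Grade 3/4 value is recorded as an AE at its laboratory grade, with or without symptoms, unless a diagnosis of at least that grade is recorded. This sets the rule for the query below. Changing the protocol itself is an amendment needing the approvals in section 11.1.

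For patients already treated, two steps do the work:

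1. **Pre-lock query.** List every on-treatment laboratory value that is Grade 3/4 on the section 7.4 scale and has no AE of matching grade, and send these to the sites. Use the 7.4 scale because SAP 10.6.2 names only CTCAE, while 7.4 grades platelets, haemoglobin and neutrophils differently and makes some patients not evaluable because of their baseline counts.
2. **Graded table.** Add to SAP 10.6.3 the worst-grade-per-patient laboratory table planned in protocol 9.4.2, with the measurements named. It comes straight from the laboratory data, so it does not depend on how a site read 7.5.3.

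The cost is one programmed query, one more table, a few more AE records and possibly a higher reported Grade 3/4 rate. Nothing in dosing or patient care changes.

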7.5.4 Deaths

Deaths that occur during the protocol-specified AE reporting period that are attributed by the investigator solely to progression of disease will be recorded on the "Trial Discontinuation" CRF and should not be reported as a SAE. All other on- trial deaths, regardless of attribution, will be recorded on an SAE Report and expeditiously reported to the Sponsor.

When recording a serious adverse event with an outcome of death, the event or condition that caused or contributed to the fatal outcome should be recorded as the single medical concept on the SAE report and Adverse Event page of the CRF. If the cause of death is unknown and cannot be ascertained at the time of reporting, record "Death NOS" on the CRF Adverse Event page.

7.5.5 Hospitalization, prolonged hospitalization, or surgery

Any AE that results in hospitalization of >24 hours or prolonged hospitalization should be documented and reported as an SAE unless specifically instructed otherwise in this protocol. There are some hospitalization scenarios (*See section 7.3*) that do not require reporting as an SAE.

7.5.6 Pre-Existing medical conditions

A pre-existing medical condition is one that is present at the start of the trial. Such conditions should be recorded on the General Medical History CRF. A pre-existing medical condition should be recorded as an AE or SAE only if the frequency, severity, or character of the condition worsens during the trial. When recording such events on an SAE Report Form and/or AE CRF, it is important to convey the concept that the pre-existing condition has changed by including applicable description.

7.5.7 Pregnancy, abortion, birth defects/congenital anomalies

Pregnancy, abortion, birth defects, and congenital anomalies are events of special interest. Please refer to pregnancy *Section 7.6.1* for specific instructions.

7.5.8 New Cancers

The development of a new primary cancer should be regarded as an AE and will generally meet at least one of the serious criteria. New primary cancers are those that are not the primary reason for the administration of the study treatment and have developed after the inclusion of the patient into the study. They do not include new lesions of the original cancer. Symptoms of metastasis or the new lesions itself should not be reported as an AE/SAE, as they are considered as disease progression.

CONFIDENTIAL Page 42 of 61

Version: 1.0, Dated 12 September 2019

7.5.9 Lack of efficacy

When there is deterioration in the condition for which the study treatment is being used, there may be uncertainty as to whether this is lack of efficacy or an AE. In such cases, unless the sponsor or reporting physician considers the study treatment contributed to the deterioration of the condition, the deterioration will be considered lack of efficacy and not an AE.

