7.1.1 Definitions of adverse events

Any untoward medical occurrence in a patient or clinical investigation subject administered a pharmaceutical product and which does not necessarily have a causal relationship with this treatment. An adverse event (AE) can therefore be any unfavourable and unintended sign (including an abnormal laboratory finding), symptom, or disease temporally associated with the use of an investigational product, whether related or unrelated to the investigational product.

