7.1.2 Recording of adverse events

All adverse events of any patient during the course of the trial will be reported in the case report form, and the investigator will give his or her opinion as to the relationship of the adverse event to trial drug treatment (i.e., whether the event is related or unrelated to trial drug administration). If the adverse event is serious, it should be reported immediately to Sponsor. Other untoward events occurring in the framework of a clinical trial are also to be recorded as AEs (i.e., AEs that occur prior to initiation of study drug that are related to a protocol-mandated intervention, including invasive procedures such as biopsies, medication washout, or no treatment run-in).

All AEs regardless of seriousness or relationship to Tenalisib, spanning from the informed consent drug until 30 calendar days after the last dose of study drug, discontinuation or completion of protocol-specific treatment as defined by the protocol for that patient, are to be recorded in the electronic Case Record Form (CRF).

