7.2 Adverse Event/Serious Adverse Event Causality Assessment

Causality is assessing the relationship of adverse event to the study drug. For this study, the causality assessment will be categorized as related and not related.

- **Related:** All toxicities should be considered related to Tenalisib unless there is a clear alternative explanation.
- **Not related:** If there is no temporal association, or another etiology has been identified as the cause, or the study drug cannot be implicated based upon the current information.

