7.3 Serious Adverse Events

7.3.1 Definitions of serious adverse events

The definitions of serious adverse events (SAEs) are given below. The principal investigator is responsible for ensuring that all staff involved in the trial is familiar with the content of this section.

CONFIDENTIAL Page 38 of 61

An SAE or reaction is defined as any untoward medical occurrence that: results in death, is immediately life-threatening, requires at least a 24-hour in-patient hospitalization or prolongation of existing hospitalization, results in persistent or significant disability/incapacity, or is a congenital anomaly/birth defect.

The definition of SAE also includes any important medical event. Medical and scientific judgment should be exercised in deciding whether expedited reporting is appropriate in other situations, such as important medical events that may not be immediately life-threatening or result in death or hospitalization, but may jeopardize the patient or may require intervention to prevent one of the other outcomes listed in the previous definition. These should also usually be considered serious. Examples of such events are intensive treatment in an emergency room or at home for allergic bronchospasm; blood dyscrasias or convulsions that do not result in hospitalization; or development of drug dependency or drug abuse. *Progression of malignancy (including fatal outcomes)*, if documented by use of appropriate method (e.g. CT) or clinically confirmed, should not be reported as a serious adverse event.

Treatment within or admission to the following facilities is not considered to meet the criteria of "in-patient hospitalization" (although if any other SAE criteria are met, the event must still be treated as an SAE and immediately reported):

- Emergency Department or Emergency Room
- Outpatient or same-day surgery units
- Observation or short-stay unit
- Rehabilitation facility
- Hospice or skilled nursing facility
- Nursing homes, Custodial care or Respite care facility

Hospitalization during the trial for a pre-planned surgical or medical procedure (one which is planned prior to entry in the trial **or** planned in advance during the course of study; and not related to the study procedure/drug), does not require reporting as a serious adverse event to the Sponsor.

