8.2 Response Evaluations and Measurements

Disease response assessments should be performed at C3D1 (\pm 7 days), C5D1 (\pm 7 days) and C8D1 (\pm 7 days), and/ or at the EOT or as clinically indicated (if clinical progression is suspected). If CT scan at Screening is negative for disease involvement in the neck, subsequent CT scans may not include neck. If CT scan at Screening is positive for disease involvement of the neck, subsequent CT scans must include neck. Disease assessment will be performed as per iwCLL guideline for CLL (Hallek *et al.* 2018) [12].

To define the response to treatment, 2 groups of parameters will be assessed and documented:

- Group A parameters: assess the lymphoid tumor load and constitutional symptoms.
- Group B parameters: assess the hematopoietic system (*Table 6*).

For complete remission (CR), all criteria given below should be met. For progressive disease, at least 1 of the criteria of group A or group B should be met; For partial remission, at least 2 of the parameters of group A and 1 parameter of group B need to improve if previously abnormal; if only 1 parameter of both groups A and B is abnormal before therapy, only 1 needs to improve.; For stable disease, all of the criteria have to be met; constitutional symptoms alone do not define PD.

Table 6: Response Criteria for CLL (iwCLL) (Hallek et al, 2018)

Group	Parameter	CR	PR	PD	SD
A	Lymph nodes	None ≥ 1.5 cm	Decrease ≥ 50% (from baseline) *	Increase ≥ 50% from baseline or from response	Change of -49% to +49%
	Liver and/or spleen size\$	Spleen size <13 cm; liver size normal	Decrease ≥ 50% (from baseline)	Increase ≥ 50% from baseline or from response	Change of -49% to +49%
	Constitutional symptoms	None	Any	Any	Any
	Circulating lymphocyte count	Normal	Decrease ≥ 50% from baseline	Increase ≥ 50% over baseline	Change of -49% to +49%
В	Platelet count	≥ 100 x 10 ⁹ /L	≥ 100 x 10 ⁹ /L or increase ≥ 50% over baseline	Decrease of ≥ 50% over baseline secondary to CLL	Change of -49% to +49%
	Hemoglobin	≥ 11.0 g/dL (untransfused and without erythropoietin)	≥ 11.0 g/dL or increase ≥ 50% over baseline	Decrease of ≥ 50% over baseline secondary to CLL	Increase <11.0 g/dL or <50% over baseline, or

CONFIDENTIAL Page 49 of 61

Version: 1.0, Dated 12 September 2019

				decrease <2 g/dL

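### Protocol 7.5.9 lets attribution decide whether an uncertain worsening of CLL is an adverse event at all, so some events may be recorded neither as an AE nor as progression

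*Protocol*

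**What the plan says.** Protocol 7.5.9 applies "When there is deterioration in the condition for which the study treatment is being used", where it is unclear whether the change is lack of efficacy or an adverse event. The doubt is settled by a default: "the deterioration will be considered lack of efficacy and not an AE". The default gives way only if someone, whether at the sponsor or the physician who reports the event, believes that Tenalisib played a part.

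Other sections of the protocol bear on the same event:

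- 7.1.1 defines an AE as any untoward occurrence, "whether related or unrelated to the investigational product".
- 7.1.2 requires recording of "All AEs regardless of seriousness or relationship to Tenalisib".
- 7.2 sets the causality rule: "All toxicities should be considered related to Tenalisib unless there is a clear alternative explanation". Its second bullet allows an event to be called not related when the drug cannot be implicated on present information.
- 7.5.3 makes any Grade 3/4 laboratory abnormality, and any clinically significant Grade 1/2 value, an AE. It makes exceptions for isolated values that the investigator confirms as without clinical significance, and for values that are a sign of a disease, where the diagnosis is recorded instead.
- 7.5.6 has a pre-existing condition recorded as an AE or SAE if it worsens, with no causality condition.
- 7.3.1 exempts progression of malignancy from SAE reporting, but only "if documented by use of appropriate method (e.g. CT) or clinically confirmed, should not be reported as a serious adverse event".
- 8.2 and Table 6 define progression. For platelets and haemoglobin it is a fall of at least 50% due to CLL, and "constitutional symptoms alone do not define PD".

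**The concern.** The overlap between disease and toxicity is wide in this population. Protocol 6.2.3 lists anaemia, thrombocytopenia, weight loss, fatigue, fever and night sweats as signs of active CLL. Section 3.5.5 names neutropenia among the events reported with Tenalisib, and Table 4 plans for both neutropenia and thrombocytopenia. Doubt about the cause of a cytopenia or a constitutional symptom is therefore foreseeable.

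Safety is a secondary objective and there is no control arm, so the handling of doubtful events feeds directly into the reported AE rates. Under 7.5.9 a doubtful event leaves the AE count without having to meet any definition of progression. Two sites facing the same event could also treat it differently, because the protocol does not say which section takes precedence.

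**Working it through.** The protocol states no figure for this point, so the check is textual, with a short comparison of thresholds.

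**1. What decides AE status.** In 7.1.1, 7.1.2 and 7.5.6, and in the Grade 3/4 sentence of 7.5.3, cause plays no part. In 7.5.9, the sponsor's or physician's view of cause decides. These cannot all hold for an uncertain worsening of CLL.

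**2. What standard exempts progression.** Section 7.3.1 asks for documentation or clinical confirmation. Section 7.5.4 asks that a death be attributed solely to progression. Section 7.5.9 exempts an event on unresolved doubt.

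**3. Toxicity grades against the Table 6 thresholds.** Percentage fall = 100 × (baseline − nadir) / baseline. In 7.4, Grade 2 is a 25–49% fall in platelets or haemoglobin, Grade 3 is 50–74% and Grade 4 is 75% or more, provided the value is below normal. The baselines below are illustrative.

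- Platelets 120 to 50 (× 10⁹/L): 70/120 = 58.3%. This is Grade 3 and passes the 50% cut for progression. If attributed to CLL it is progression. If that attribution is not established, it is not.
- Platelets 120 to 65: 55/120 = 45.8%. This is Grade 2 and lies inside the stable-disease band of ±49%.
- Haemoglobin, baseline 12 g/dL: progression needs 12 × 0.50 = 6.0 or lower; Grade 2 begins at 12 × 0.75 = 9.0; the stable-disease row allows a fall of less than 2, so a value above 10.0. A value above 6.0 and up to 10.0 meets neither the progression threshold nor the stable-disease limit on a decrease.

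**4. Where the 7.5.9 default leaves each kind of event.**

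| Uncertain worsening, drug not thought to contribute | AE under 7.5.9? | Progression under Table 6? |
|---|---|---|
| Constitutional symptoms alone | No | No |
| Neutropenia | No | No; neutrophil count is not a Table 6 parameter |
| Haemoglobin or platelet fall below 50% | No | No |
| Fall of at least 50%, not established as due to CLL | No | No |
| Fall of at least 50%, attributed to CLL | No | Yes |

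In the third row, 7.5.9 makes a difference only for clinically significant values. Other Grade 1/2 values would go unrecorded under 7.5.3 in any case.

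**5. Whether the SAP recovers these events.** SAP 10.6.2 builds its AE and Grade 3/4 tables from recorded AEs. SAP 10.6.3 plans descriptive statistics of absolute laboratory values and listings, with no table by grade. Protocol 9.4.2 promises worst grades per patient for selected laboratory measurements, but SAP 10.6.3 does not carry that through. An unrecorded cytopenia is visible in a listing and missing from every tabulated rate.

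**6. Sensitivity.** SAP section 6 reports 21 patients enrolled. If all 21 were dosed, and so form the safety population, each patient whose only qualifying event goes unrecorded changes a rate by 1/21 = 4.8 percentage points. The documents do not say how many such patients there are.

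**The case against.** The strongest defence is that 7.5.9 is narrow and deliberate. It covers only worsening of CLL, and the sponsor or physician can restore AE status. Keeping disease progression out of the AE count agrees with 7.3.1, 7.5.4 and 7.5.8. Section 7.5.1 has symptoms that cannot be assigned to a single diagnosis recorded individually, 7.5.3 already covers Grade 3/4 values, and laboratory listings will show the cytopenias. The study has also closed after Stage 1, so rewriting the protocol cannot change what was collected.

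Much of this stands, and it rules out three stronger readings.

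- A reader might infer that 7.5.9 is the reverse of 7.2. It is not. Section 7.2 governs causality rather than AE status, and its second bullet leans the same way as 7.5.9. An assessor who applies its first bullet first has found the drug related, which triggers the exception in 7.5.9 and makes the event an AE. The protocol gives no order, so sites may differ, but one assessor need not be in contradiction.
- A reader might infer that cytopenias in general disappear. Haemoglobin and platelet falls of at least 50% attributed to CLL are progression.
- A reader might attach a figure to the bias. Any count of affected patients would be invented.

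The defence does not remove the conflict. The neighbouring exemptions rest on documented, confirmed or sole attribution, whereas 7.5.9 rests on doubt. Neither 7.5.1 nor 7.5.3 is stated to prevail over it, and the sign-of-disease exception in 7.5.3 can be read as supporting it. Listings do not enter the Grade 3/4 rates.

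**Conclusion.** The point holds as a recording inconsistency that needs to be reconciled. Section 7.5.9 makes AE status for an uncertain worsening of CLL depend on attribution, against 7.1.1, 7.1.2, 7.5.6 and the Grade 3/4 rule of 7.5.3, and on a looser standard than 7.3.1. The events at risk are those in the first four rows of the table.

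The effect can only lower AE counts relative to the recording rule in 7.1.2. Its size is unknown: the documents give no frequencies, and it depends on how sites read 7.5.9 beside 7.5.3 and 7.2. The 4.8 points per patient is a scale for judging the effect, not an estimate, and it assumes a safety population of 21. The response-rate decision rule is not affected. The correction is worth making because it is cheap and bears on a stated secondary objective.

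**What to change.** Amend the recording rule as follows.

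- Limit 7.5.9 to progression that is documented under Table 6 or clinically confirmed in the sense of 7.3.1.
- Replace its default with: *if it is uncertain whether a deterioration is progression or an adverse event, record it as an adverse event and assess causality under 7.2.*
- State that 7.5.3 prevails over 7.5.9 for Grade 3/4 laboratory values.

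Since enrolment has ended, apply this through data review before database lock. Query every Grade 3/4 haematology value, and every documented deterioration, that has no matching AE record, and let the investigator either record the event or confirm that an exception in 7.5.3 applies. Add to SAP 10.6.3 the worst-grade laboratory table promised in protocol 9.4.2, using the iwCLL grading named there. That table does not depend on AE recording.

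The cost is a few sentences, one round of queries and one table. Somewhat more AEs will be recorded, some of them disease-related and labelled not related. Constitutional symptoms will be harder to recover in retrospect than laboratory values. If the database is already locked, produce the laboratory table and describe the 7.5.9 rule in the study report as a limitation of the AE counts.
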